6.2. REPEATED ANALYSIS VISITS AND ANALYSIS TIME POINTS

After baseline and except if unscheduled or being part of a specific profile, no replications of analysis visits or analysis time points should exist. Specifications for unscheduled analysis visits are described in the next section.

6.3. UNSCHEDULED ANALYSIS VISITS

Refer to sections [5.2](#) and [5.3](#).

6.4. SELECTION OF VALUES PROVIDED IN DIFFERENT UNITS

When values like results or normal limits are provided in conventional original units as well as in standardized units, only the expressions in standardized units will be considered for all analysis purposes. Data stored in original, conventional units will be disregarded.

7. HANDLING OF DATA

7.1. HANDLING OF MISSING DATA

7.1.1. Missing Records or Missing Values

No imputations will be done in case of missing records (visits) or missing values like results, normal limits etc.

7.1.2. Missing Dates or Times or Partially Known Dates or Times

No imputations will be done in case of missing date(time) fields, nor for the missing parts of partially known date(time) fields. If this causes imprecisions, a worst-case consideration will be done, like assuming persistence if an end date is missing, or replicating records over different analysis periods.

7.2. HANDLING OF SECONDS IN TIME FIELDS

The analysis will consider times only in hours and minutes. Seconds in the time of a record, if any, will be cut-off before analysis and disregarded.

7.3. CALCULATION AND PRESENTATION OF DESCRIPTIVE STATISTICS

Any descriptive statistics (and summary graphics) for continuous parameters will be printed only when the number of observations is two or more, except for PK analysis where specific rules are described below. Single observations will only be listed.

In the general subject information, efficacy and safety parts of the analysis, descriptive statistics will include:

- the number of non-missing observations (n);
- the arithmetic mean;
- the standard error (SE);
- the standard deviation (SD);
- the median;
- the minimum and maximum values;
- 95% confidence interval of the mean (only when requested).

For each parameter concerned, the number of decimal places printed for all descriptive statistics will be the same maximum number of decimals of the actual analysis values of the parameter, except:

- mean, median, confidence interval of the mean: one more decimal place;
- SD, SE: two more decimal places.

For PK part of the analysis, descriptive statistics will include:

- the number of non-missing observations (n);
- the number of data points above the limit of quantification (only applicable for concentrations);
- the arithmetic mean;
- the standard error (SE)
- the standard deviation (SD)
- the median;
- the minimum and maximum values;
- the coefficient of variation (CV%)
 - = 100 x (standard deviation/arithmetic mean);
- the geometric mean
 - = exp(arithmetic mean of ln-transformed data);
- the geometric coefficient of variation (geometric CV%)
 - = 100 x $\sqrt{e^{(\text{standard deviation of ln-transformed data})^2} - 1}$

If less than 50% of the subjects have quantifiable values, only the number of subjects with data, number of data points above the lower limit of quantification (LLOQ), the arithmetic mean, median, minimum, and maximum will be presented with the original calculated value. The other descriptive statistics will be listed as “NC” (not calculated).

If the calculated mean is below the lower limit of quantification (BLOQ), then it will be presented as “BLQ”.

The concentration levels will be presented in the original unit. Concentrations will be presented with:

- 2 decimals for values < 10
- 1 decimal for values > 10 and < 1000
- No decimals for value > 1000.

The descriptive statistics should be rounded to the same number of decimals as the individual values.

7.4. PRESENTATION OF INFERENCE STATISTICAL ANALYSIS

Refer to section 10 for more details.

7.5. CALCULATION AND PRESENTATION OF FREQUENCIES

Frequencies of categorical parameters will be calculated only for the actually observed cases. All observed frequencies from n = 1 on will be printed.

7.6. CALCULATION AND PRESENTATION OF PERCENTAGES

Frequencies and percentages will be generated for categorical parameters. Only non-missing values will contribute to the denominator when computing percentages.

The default denominator is the number of subjects in a treatment group, but can be further restricted as applicable. The denominator used should always be described in footnotes.

7.7. CATEGORIZATION OF RESULTS OF CONTINUOUS PARAMETERS

Categorization of the results of continuous parameters may apply in different sections of the analysis. Categorizations will always be determined after the analysis values of the parameters concerned have been established. Rounding of analysis values will not be done.

7.8. HANDLING OF VALUES BELOW OR ABOVE A THRESHOLD

- In the general subject information and in the safety part of the analysis: when results or normal limits of continuous parameters are expressed in the database as being below or above a detection limit (e.g. “<4”, “>1000”) and not available in pure

numerical form, the analysis value will be the value of the detection limit itself plus or minus one precision unit (e.g. 3, 1001, respectively). The values before this imputation will only be shown in listings.

- In the PK and PD [REDACTED] parts of the analysis:
 - o Values below the quantification limit will be imputed by 0 for the calculation of descriptive statistics, PK analyses and graphical presentation except for the geometric mean and the geometric CV, where it will be imputed as LLOQ/2.
 - o Values below the quantification limit will be listed as “BLQ”.

7.9. SOFTWARE, PROCEDURES AND STANDARDS

7.9.1. Software

SAS version 9.4 (or higher) will be used for programming.

Phoenix WinNonLin version 6.4 (or higher) will be used for PK derivations.

7.9.2. Procedures

This statistical analysis will comply with ICH regulations, in particular: (ICH-E3), (ICH-E6) and (ICH-E9).

The following Galapagos statistics, programming and pharmacokinetics SOPs will be followed:

- SOP-CLI-001: Developing Clinical Study Documents (version 2.0)
- SOP-BIOM-002: [Managing Biostatistics Activities and Programming](#) (version 1.0)

The following [REDACTED] statistics and pharmacokinetics SOPs will be followed:

- Statistics:
 - BST002-SOP Version 2.0
 - BST004-SOP Version 2.0
 - BST005-SOP Version 2.0
 - BST007-SOP Version 1.0
 - PRG001-SOP Version 2.0
- PK:
 - PK003-SOP Version 3.0
 - PK004-SOP Version 2.0
 - PK006-SOP Version 2.0

7.9.3. Standards for Data Storage and for Analysis Layout

The database source for this analysis is expected to follow the CDISC SDTM model.

The analysis derived datasets will follow the CDISC ADaM 2.1 model, based on the ADAMIG version 1.1.

The general layout of the tables, listings and figures of this analysis will follow the Sponsor Mock TLFs document (separate document).

8. STATISTICAL METHODS

8.1. PLANNED ANALYSES, PROTOCOL AMENDMENTS INCLUDED

The SAP will be finalized before the final analysis. All relevant data collected in this clinical study will be documented using summary tables, figures, and subject data listings.

8.1.1. Final Analysis

The full results will be summarized in a clinical study report (CSR) after all subjects have completed their study participation (i.e. Day 169 or discontinued earlier).

8.1.2. Sample Size

Refer to section 7.1 of the protocol.

8.1.3. General Statistical Considerations

In addition to tabulated descriptive statistics, graphical data displays may be used to summarize the data. Unless otherwise noted, inferential statistics will be interpreted at the 2-sided 5% significance level.

No analysis by center or country will be performed, unless otherwise specified.

8.1.4. Analyses of Demographics and Baseline Characteristics

Subject disposition (including reasons for early discontinuation), protocol deviations, demographics, baseline characteristics, medical history, concomitant therapies will be analyzed descriptively based on the safety analysis set.

8.1.5. Analysis of Efficacy Parameters

Efficacy endpoint analyses will be performed using the FAS. For subjects who use rescue medication, all data collected after administration of the rescue medication will be excluded from efficacy analysis (this means that data collected on the day of rescue medication administration will be used for efficacy analysis). Subject data will be handled as if the subject left the study at the moment the rescue medication started. Efficacy assessment performed after the start of the rescue medication will only be listed.

Efficacy data () will be summarized using descriptive statistics of actual values, changes from baseline, and percent changes from baseline, with 95% confidence intervals. Binary and categorical endpoints () will be presented by number (percent) of subjects per treatment group and visit.

Percent changes from baseline for continuous endpoints () will be analyzed using an mixed-effects model for repeated measures. The model will include

treatment and visit as fixed effects, country and baseline value (continuous) as covariates, and treatment-visit as interaction term.

Binary parameters () will be analyzed using a generalized estimating equation model. The model will include treatment and visit as fixed effects, country and baseline value (continuous) as covariates, and treatment-visit as an interaction term. Pairwise comparisons to placebo will be explored as well, without multiplicity correction.

The primary approach will be the observed case approach without imputation of missing data.

Additional exploratory analyses and graphical presentations may be performed when deemed useful to better understand the data.

All other efficacy endpoints will only be listed

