4.5.3.2.1. Topical Corticosteroids (TCS)

Subjects will not use any TCS for at least 7 days prior to the baseline (Day 1) visit.

From Day 1 onwards, all subjects will apply concomitant open-label, once daily treatment with TCS as follows:

- Medium potency TCS (e.g. Triamcinolone 0.1% cream or Mometasone furoate 0.1% cream or another sponsor approved TCS) to be used as per approved label.
- Other topical medications, such as a lower potency TCS or TCI, may be used to treat AD lesions located on the face, flexural, and genital areas as per approved label.
- Once control has been achieved (lesions have cleared or almost cleared), TCS or TCI application to areas from which lesions have (almost) cleared, will, under the supervision of the investigator, be limited to twice weekly in intervals of 3-4 days until the end of the treatment period (D57).
- During the follow-up period (D57 to D169), topical treatment of residual active AD lesions may continue as needed at the investigator's discretion. This treatment can be stepped up or stepped down as clinically indicated per investigator's discretion.
- During the follow-up period (D57 to D169), in the event of an AD flare, initiation or escalation of TCS therapy will be recorded as rescue therapy in the follow-up period.

 All TCS (and TCI if used) use will be recorded daily by the subject in a diary from screening visit onwards and throughout the study and will be reviewed at each onsite visit by the investigator.

Detailed instructions on TCS management will be described in a separate study reference manual.

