Every effort should be made to keep subjects in the study and on treatment. However, the investigator can consider stopping the treatment with IMP, preferably after consultation with the sponsor's study physician, in case of concerns about the subject's safety, major protocol noncompliance, serious or severe AEs or worsening of the disease condition,

Galapagos MOR106-CL-204

which in the investigator's opinion needs an alternative treatment approach not being covered in the clinical study (e.g. rescue medication).

When study treatment is discontinued, the subject will be requested to return for Early Treatment Discontinuation (ETD) visit and will be asked to continue the follow-up period until end of study.

Subjects will be informed prior to clinical study entry that they are allowed to withdraw from the clinical study. At any time and for any reason, a subject's participation in the clinical study may terminate at his/her request without prejudice to his/her future medical care. The subject will be encouraged to share the reason(s) for withdrawal so this can be documented in the source documents, and to complete the ED/ETD visit and follow-up visits for safety assessments, but will not be obliged to do so.

Subjects who withdraw from the clinical study without contact with the site (lost-to-followup) should be contacted by the site so that their health status can be assessed and documented in the source documents. The site should make every effort to understand whether the subject is alive, including checking the medical records and contacting general practitioner or relatives, if necessary. All attempts must be documented in the source documents.

The sponsor has the right to terminate the clinical study at any time in case of safety concerns or if special circumstances concerning the IMP or the company itself occur, making further treatment of subjects impossible. In this event, the investigator(s) and relevant authorities will be informed of the reason for clinical study termination.

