7.3.6. Analyses of Efficacy Parameters

Efficacy endpoint analyses will be performed using the Full Analysis Set. Efficacy data will be summarized using descriptive statistics of actual values, changes from baseline, and percent changes from baseline, with 95% confidence intervals. Binary and categorical endpoints will be presented by number (percent) of subjects per treatment group and visit.

Changes and percent changes from baseline for continuous endpoints

will be analyzed using an mixed-effects model for repeated measures. The model will include terms for treatment and visit as fixed effects, country and baseline value (continuous) as covariates, and treatment-visit as interaction term.

Binary parameters **and the second sec**

Time to event endpoints will be presented using the Kaplan-Meier estimates and the two treatment groups will be compared using a log-rank test.

More details will be provided in the SAP.

The primary approach will be the observed case approach without imputation of missing data. In case of unexpected high attrition rates, sensitivity analyses including the use of multiple imputation methods may be considered. If more than 10% of subjects included in the full analysis set population are excluded from the per protocol analysis, a per protocol analysis will be performed.

Additional exploratory analyses and graphical presentations may be performed when deemed useful to better understand the data and will be detailed in the SAP.

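### On the readable text, subjects given rescue leave later responder percentages and the GEE, so observed-case rates, mainly after Day 57, are likely too high if those subjects would have responded less often

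*SAP*

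**What the plan says.** **Rescue.** SAP 8.1.5 sets one rule for all efficacy data, with no exception for binary endpoints: assessments after rescue are listed but not analysed. "Subject data will be handled as if the subject left the study at the moment the rescue medication started". The day of rescue itself still counts: "this means that data collected on the day of rescue medication administration will be used for efficacy analysis".

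**Missing data.** The same section continues: "The primary approach will be the observed case approach without imputation of missing data". SAP 7.1.1 is general: "No imputations will be done in case of missing records (visits) or missing values like results, normal limits etc". Protocol 7.3.6 also makes observed case the primary approach and adds: "In case of unexpected high attrition rates, sensitivity analyses including the use of multiple imputation methods may be considered". The readable SAP does not carry that option over.

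**Percentages and model.** SAP 7.6 says: "Only non-missing values will contribute to the denominator when computing percentages". Its next sentences name the treatment group size as the default denominator, allow it to be restricted, and ask for a footnote stating which was used. Binary endpoints are shown as number and percent by arm and visit. They are modelled by GEE with treatment, visit, country, baseline value and treatment-by-visit.

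**What counts as rescue.** For follow-up (Day 57 to Day 169), Protocol 4.5.3.2.1 says: "in the event of an AD flare, initiation or escalation of TCS therapy will be recorded as rescue therapy in the follow-up period". Protocol 4.5.4 mentions rescue medication once more, as an example when IMP may be stopped because worsening disease "needs an alternative treatment approach not being covered in the clinical study (e.g. rescue medication").

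**The concern.** Read together, these rules make a rescued subject missing at every later visit, and the reason for being missing is a flare. Subjects still counted at late visits are those who did not need rescue. A responder percentage among them describes a group selected for doing well.

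The GEE does not in general repair this. Without weighting for missingness, it needs missingness unrelated to outcome given the model covariates. Here those are treatment, visit, country and baseline value, and removal for a flare is unlikely to meet that condition. The continuous endpoints are less exposed, because a likelihood-based repeated-measures model uses each subject's values up to the day of rescue and rests on the weaker missing-at-random assumption.

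At stake is how the late responder rates, and the planned pairwise comparisons with placebo on binary endpoints, can be read. Without a summary of rescue by arm, a reader cannot easily separate response from selection.

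**Working it through.** The plan gives no efficacy, rescue or response figure to reproduce. Its one sample-size probability (Protocol 7.1: 87% chance of at least one adverse event of 5% incidence in 40 subjects) does reproduce, as 1 − 0.95^40 = 0.871, but it has no bearing here.

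**Inputs.** From the documents: 40 subjects on MOR106 and 20 on placebo. Assumed: all rescue shares and response counts. Attendance is taken as otherwise complete.

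**Step 1: excess under the SAP's own reading.** Let q be the share rescued, obs the response rate among those not rescued, and p the rate the rescued would have had without rescue. The all-subject rate is (1 − q) × obs + q × p, so

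excess = obs − [(1 − q) × obs + q × p] = q × (obs − p).

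With 12 responders on MOR106 among those not rescued:

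| q | obs | p = 0 | p = 0.1 | p = 0.2 | p = obs |
|---|---|---|---|---|---|
| 10% | 12/36 = 33.3% | 3.3 | 2.3 | 1.3 | 0 |
| 20% | 12/32 = 37.5% | 7.5 | 5.5 | 3.5 | 0 |
| 30% | 12/28 = 42.9% | 12.9 | 9.9 | 6.9 | 0 |

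Excesses are in percentage points. If p exceeded obs, the sign would reverse.

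**Step 2: the denominator.** With 8 of 40 rescued, the non-missing rule gives 12/32 = 37.5%. The default denominator in SAP 7.6 would give 12/40 = 30.0%, which in effect counts the rescued as non-responders, while the GEE would still use 32 subjects at that visit. Table and model would then answer different questions.

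**Step 3: arm difference under the SAP's own reading.** Take 12 responders on MOR106, 4 on placebo, and p = 0.1 in both arms.

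- 10% rescued on MOR106, 30% on placebo: observed 12/36 − 4/14 = 4.8 points. All-subject rates are 12/40 + 0.1 × 0.1 = 31% and 4/20 + 0.3 × 0.1 = 23%, a difference of 8.0. Shift −3.2.
- 30% on MOR106, 10% on placebo: observed 12/28 − 4/18 = 20.6 points. All-subject rates are 33% and 21%, a difference of 12.0. Shift +8.6.

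**Step 4: difference with rescue counted as non-response (p = 0).** The reference is 12/40 − 4/20 = 10.0 points. Observed case gives 12/36 − 4/18 = 11.1 (10% rescued in both arms), 12/32 − 4/16 = 12.5 (20% in both), 4.8 (10% vs 30%) and 20.6 (30% vs 10%). Shifts run from −5.2 to +10.6.

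**Step 5: sampling error.** SE = √(0.3 × 0.7/40 + 0.2 × 0.8/20) = 0.115, and 1.96 × 0.115 gives a half-width of about 22.6 points. Every shift above lies inside it.

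**The case against.** The strongest reply is that this is a choice of target, not an error. The SAP says what it does with rescued subjects, and observed case is also the protocol's primary approach. Counting rescue as non-response answers a different question. It also brings investigator discretion into the endpoint, since topical treatment in follow-up may be stepped up or down at the investigator's judgement. This stands, and it is why non-response belongs in a sensitivity analysis. It does not remove the problem, because Step 1 shows a bias under the SAP's own target whenever p is below obs.

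Four further limits stand:

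- **Redaction.** SAP 7.4 sends inferential detail to section 10, whose derivations are blacked out, as are some entries in SAP 8.2.1. A reader might infer that the plan has no responder rule for rescue. The documents do not support that, since one may sit in the redacted text.
- **Denominator.** SAP 7.6 is not settled. The restriction to non-missing values is the more natural reading, but the default in the next sentence points the other way.
- **Timing.** A reader might infer that visits up to Day 57 are equally affected. SAP 8.1.5 has no time limit, but the explicit rescue definition covers follow-up only, and Protocol 4.5.4 offers only a parenthetical example.
- **Existing safeguards.** Day-of-rescue data are kept, later assessments are listed, and Listing 16.2.4.8 shows rescue by arm and subject. With about 60 subjects, a non-responder count could be rebuilt by hand. It would then be improvised after the fact, not pre-specified.

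**Conclusion.** The point holds on the readable text as a low-stakes improvement. Followed as written, SAP 8.1.5 with 7.1.1 and 7.6 removes rescued subjects from binary summaries and the GEE after the day of rescue. Because follow-up rescue is triggered by a flare, the remaining group is selected on outcome.

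A reader might infer that the reported rates necessarily overstate response. They do so only if rescued subjects would have responded less often than the others. That is plausible after a flare, but the documents do not show it. A reader might also take −5.2 to +10.6 points as the likely error in the arm difference. That range rests on assumed rates and on a non-response target the SAP did not choose. Under the SAP's own reading with p = 0.1, the two unequal-rescue examples give −3.2 and +8.6. The direction depends on which arm is rescued more, and the true size is unknown.

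Efficacy is neither a primary nor a secondary endpoint, and the SAP was already cut back after development in atopic dermatitis stopped for futility. Safety, PK and ADA conclusions do not change.

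**What to change.** - Keep the observed-case analysis as the primary approach, as the protocol and SAP have it.
- In SAP 8.1.5, pre-specify one sensitivity analysis for binary endpoints: count a subject as a non-responder at scheduled visits after the day rescue starts, and keep the subject in the denominator and the GEE.
- In SAP 7.6, state which denominator applies to responder percentages.
- Add one table of rescue use by arm and visit through Day 169, summarising what Listing 16.2.4.8 shows subject by subject.
- If section 10 already contains a rescue rule for responders, reconcile it with 8.1.5 instead of adding a second one.

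The rule for continuous endpoints can stay, and nothing here touches when rescue is given. The cost is some SAP wording, one derivation and one small table. The downside is a little more programming and lower response rates in the sensitivity analysis.
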